9.1.2 Serious Adverse Event

An SAE is defined as any untoward medical occurrence that at any dose:

- **Results in death:** The event must be the cause of death for the SAE to meet this serious criterion.
- **Is life-threatening:** The term “life-threatening” refers to an event in which the subject was at risk of death at the time of the event; it does not refer to an event that hypothetically might have caused death if it had been more severe.
- **Requires in-patient hospitalization or prolongation of existing hospitalization:** CSL considers “hospitalization or prolongation of existing hospitalization” for ≥ 24 hours as the defining criterion for an SAE. Hospital admissions for planned surgery or for normal disease management procedures (eg, chemotherapy) are not considered defining criteria for SAEs.
- **Results in persistent or significant disability or incapacity.**
- **Is a congenital anomaly or birth defect.**
- **Is medically significant:** A medically significant event is defined as an event that does not necessarily meet any of the SAE criteria, but which is judged by a physician to potentially jeopardize the subject or require medical or surgical intervention to prevent one of the above outcomes listed as an SAE criterion.

AEs that do not fall into the above categories are defined as nonserious AEs.

9.1.3 Adverse Event of Special Interest

There are several AEs that will be monitored closely as AEs of special interest (AESIs) to allow for an adequate risk-benefit evaluation of CSL312 during the study. Additional data may be requested for these events.

The AESIs for this study are:

- Bleeding events that are abnormal in the opinion of the investigator
- TEEs
 - Non-systemic thrombosis (eg, localized thrombosis associated with vascular access) is not considered an AESI
- Severe hypersensitivity including anaphylaxis

The reporting requirements for AESIs are detailed in [Section 9.6.2](#)

9.2 Severity of Adverse Events

The severity of each AE (ie, nonserious and serious AEs) is to be assessed by the investigator as shown in Table 9.

Table 9 Severity of Adverse Events

Severity	Definition
Mild	A type of AE that is usually transient and may require only minimal treatment or therapeutic intervention. The event does not generally interfere with usual activities of daily living.
Moderate	A type of AE that is usually alleviated with additional specific therapeutic intervention. The event interferes with usual activities of daily living, causing discomfort but posing no significant or permanent risk of harm to the subject.
Severe	A type of AE that interrupts usual activities of daily living, or significantly affects clinical status, or may require intensive therapeutic intervention.

AE = adverse event; CDISC SDTM Severity Intensity Scale for Adverse Event Terminology.

9.3 Causality of Adverse Events

The causal relationship of an AE to the investigational product **must always be assessed** by the investigator. All AEs will be classified as either **related** or **not related** to the investigational product. If a causality assessment is not provided for an AE (including an SAE), that AE will be considered related to the investigational product.

The degree of certainty with which an AE is attributed to investigational product or an alternative cause (eg, natural history of the underlying disease, concomitant therapy) will be determined by how well the event can be understood in terms of:

- Known pharmacology of investigational product.
- Clinically and / or pathophysiologically plausible context.
- Reaction of a similar nature previously observed with similar products, or reported in the literature for similar products as being product related (eg, headache, facial flushing, pallor).

- Plausibility supported by the temporal relationship (eg, the event being related by time to administration or termination of treatment with investigational product, drug withdrawal, or reproducible on rechallenge).

9.4 Observation Period for Adverse Events

The observation period for the reporting of AEs and SAEs for an individual subject will start at the time at which written informed consent for participation in the current study is obtained and ends with the Follow-up Telephone Call.

If the investigator becomes aware of an SAE that started after the observation period has finished, and there is at least a possible causal relationship with the investigational product, the event must be reported to CSL (see [Section 9.6.3](#)).

9.5 Follow-up of Adverse Events

Every effort should be made to follow AEs until resolution or stabilization. Ongoing, nonserious AEs that have not resolved or stabilized will be followed until the subject completes the study. SAEs will be followed until the AE resolves, stabilizes, or the subject is lost to follow-up.

9.6 Adverse Event Reporting

9.6.1 Adverse Events

At each clinical evaluation, the investigator (or delegate) will determine whether any AEs have occurred. All AEs are to be recorded in the eCRF. If known, the medical diagnosis of an AE should be recorded in preference to the listing of individual signs, laboratory findings, and / or symptoms. The investigator must follow up on the course of an AE until resolution or stabilization. If an AE is ongoing after the Follow-up Visit, the AE will continue to be followed until resolution, stabilization, or the subject is lost to follow-up.

If, during the study period, a subject presents with a preexisting condition that was not noted at the time of study entry, the condition should be retrospectively recorded in the Medical History eCRF.

9.6.2 Adverse Events of Special Interest

Adverse event of special interest must be reported as AEs in the subject's eCRF. Additional data may be requested in the eCRF for these events. Serious and nonserious AESIs must be reported following the procedures for expedited reporting as described for SAEs (see Section 9.6.3).

9.6.3 Serious Adverse Events

This study will comply with all applicable regulatory requirements and adhere to the full requirements of ICH Topic E2A (Clinical Safety Data Management: Definitions and Standards for Expedited Reporting).

For SAEs occurring during the study, the investigator or delegate will enter all relevant information in the eCRF.

All SAEs that occur during the course of the study, whether or not causally related to the investigational product, must be entered into the eCRF immediately (within 24 hours of the investigator's becoming aware of the event). Assessment of causality to the investigational product must be included.

AEs occurring in the period between the time when the subject gave written informed consent and the first exposure to investigational product, and that meet 1 or more of the seriousness criteria, must be entered into the eCRF in the same manner as other SAEs and will be included in the clinical study database.

Any SAE that occurs after the EOT Visit that is considered to be causally related to investigational product must be **reported immediately (ie, within 24 hours of the investigator becoming aware of the event) to CSL**. Such events are not entered into the eCRF.

The minimum reporting requirements for reporting of SAEs include:

- Subject identification number
- Suspected medicinal product and / or procedure
- Event term
- Reporting source identification

If the minimum requirements for reporting are fulfilled, the investigator should not wait to receive additional information to fully document the event.

In addition, the investigator must:

- Report all SAEs to the relevant IRB / IEC within the timeframe specified by the IRB / IEC
- If the subject is an active participant in the study:
 - Enter follow-up information in the eCRF until the SAE has resolved, or, in the case of permanent impairment, until stabilized
 - Ensure that the causality assessment for all SAEs is entered in the eCRF
- If the subject is no longer participating in the study, report the follow-up information to CSL

In cases of death, the investigator should supply CSL and the IRB / IEC (as applicable) with any additional information as it becomes available (eg, autopsy reports and detailed medical reports).

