ADA = antidrug antibody; AE = adverse event; ALT= alanine aminotransferase; aPTT = activated partial thromboplastin time; AST = aspartate aminotransferase; BMI = body mass index; CCL = C-C motif chemokine ligand; CK = creatinine kinase; CPa9-HNE = neo-epitope of calprotectin generated by human neutrophil elastase; CPK = creatinine phosphokinase; CRPM = neo-epitope of matrix metalloproteinase-mediated degradation of C-reactive protein; CSL = CSL Behring; CXCL = C-X-C motif chemokine ligand; DL_{CO} = diffusing capacity of the lungs for carbon monoxide; ECG = electrocardiogram; EOI = end of the infusion; EOT = end of treatment; EW = early withdrawal; FU = follow-up; GGT = gamma glutamyltransferase; HDL = high-density lipoprotein; hs-CRP = high-sensitivity C-reactive protein; IPF = idiopathic pulmonary fibrosis; IL=interleukin; INR = international normalized ratio; IRT = interactive response technology; IV = intravenous; LDH= lactate dehydrogenase; LDL = low-density lipoprotein; MCH = mean corpuscular hemoglobin; MCHC = mean corpuscular hemoglobin concentration; MCV = mean corpuscular volume; PAI-1 = plasminogen activator inhibitor 1; PD = pharmacodynamic; pF1+2 = prothrombin fragment; PFT = pulmonary function test; PK = pharmacokinetic; Pro-Fib = biomarker specifically targeting the thrombin-mediated conversion of fibrinogen into fibrin; PT = prothrombin time; RBC = red blood cell; RDW = red cell (erythrocyte) distribution width; RNA seq = ribonucleic acid sequencing; SC = subcutaneous; SP-A = surfactant protein A; SP-D = surfactant protein D; TN-C = tenascin-C; TSP-1 = thrombospondin 1; VEGF = vascular endothelial growth factor; VICM = neo-epitope of matrix metalloproteinase-mediated degradation of citrullinated vimentin; WBC = white blood cell.

Notes for the Schedule of Assessments:

- A. Eligible subjects must discontinue all prohibited medications \geq 28 days (or 5 half-lives) before randomization.
- B. The Follow-up Visit will be a telephone call conducted on Day 154 (\pm 5), approximately 90 days after the last administration of investigational product, to collect data on AEs (including acute exacerbations of IPF) and concomitant medications since the previous study visit.
- C. EOT / EW Visit. If a subject withdraws from the study before the Week 14 Visit, the subject will be asked to return to the study site to complete the EOT assessments.

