8.5.5 End-of-Treatment Visit

The scheduled end of study participation for an individual subject occurs with completion of the EOT Visit on Day 92 ± 2 days, after which no further study-related procedures will be performed.

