8.5.6 Follow-up Telephone Call

On Day 154 (\pm 5 days), the investigator (or delegate) will contact the subject by telephone to collect data on AEs (including acute exacerbation of IPF symptoms) and concomitant medications. The Follow-up Telephone Call should be scheduled to occur 90 days after the last administration of investigational product.

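### Protocol 9.6.3 keeps related SAEs after the EOT Visit (Day 92) out of the eCRF, although SAE observation runs to the Day 154 telephone call

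*Protocol*

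**What the plan says.** **Observation period.** Protocol 9.4 starts AE and SAE reporting at consent and says that it "ends with the Follow-up Telephone Call". Its rule limited to possibly related events covers only SAEs that begin after that period is over. Note B to the Schedule of Assessments dates the call: "The Follow-up Visit will be a telephone call conducted on Day 154" (±5 days). Section 8.5.6 adds: "The Follow-up Telephone Call should be scheduled to occur 90 days after the last administration of investigational product". Both places give the call the task of collecting AEs, including acute exacerbations.

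**Entry in the eCRF.** Protocol 9.6.1 puts all AEs in the eCRF. Section 9.6.2 puts AESIs there too and adds: "Serious and nonserious AESIs must be reported following the procedures for expedited reporting as described for SAEs". Section 9.6.3 first requires every SAE during the study, regardless of causality, to be entered within 24 hours of awareness.

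**The exception.** Section 9.6.3 then says: "Any SAE that occurs after the EOT Visit that is considered to be causally related to investigational product must be" reported to the sponsor within 24 hours, followed by "Such events are not entered into the eCRF". The trigger is the EOT Visit (Day 92 ± 2), not the telephone call.

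**End of participation.** Section 8.5.5 places the scheduled end of a subject's participation at the EOT Visit, "after which no further study-related procedures will be performed". Sections 3.1, 3.4 and 3.7 instead carry the study through the call or last contact.

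**SAP.** Section 8.4 defines a post-treatment period from Day 92 to the Day 154 call. Section 11.2 lists all AEs and all SAEs, but summarises only TEAEs that start by the end of the Treatment and Observation Period. Protocol 10.3.3 gives TEAEs a start and no end.

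**The concern.** Safety is the primary objective, and SAEs and AESIs are named components of the primary endpoint. The rule in 9.6.3 for related SAEs looks like one meant for events after observation has closed, but it takes effect at Day 92, while observation is still open. A site that follows it keeps out of the eCRF the late serious events it considers drug-related, which are the ones a safety study most needs to hold. The result is perverse: a related nonserious event in the window is entered under 9.6.1, while a related serious event is not. A serious AESI judged related gets opposite instructions from 9.6.2 and 9.6.3.

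This is a fault in collection. No change to the SAP alone can list or tabulate an event that the clinical database does not contain.

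**Working it through.** **1. Inputs.** Last dose Day 64 (protocol 8.5.3). EOT Visit Day 92 ± 2 (8.5.5). Telephone call Day 154 ± 5, to fall 90 days after the last dose (8.5.6). SC half-life about 18 days and Tmax about 7 days (1.2.3.1). Bioavailability about 50% (3.3.2).

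**2. The plan's own date.** 64 + 90 = 154. This matches.

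**3. Length of the gap.** 154 − 92 = 62 days. With visit windows, the shortest is (154 − 5) − (92 + 2) = 55 days and the longest is (154 + 5) − (92 − 2) = 69 days. The gap is 62 / (154 − 1) = 62/153 = 41% of the time from first dose to the call, and 62/90 = 69% of the follow-up after the last dose.

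**4. Whether the window matters pharmacologically.** Day 92 is 92 − 64 = 28 days after the last dose, which is one dosing interval, so the window opens at a trough. As an illustration only, take a one-compartment model with k = ln 2 / 18 = 0.0385 per day and ka = 0.356 per day (which gives Tmax = 7 days). Each SC dose contributes 600 × 0.5 × ka/(ka − k) × (e^(−kt) − e^(−ka·t)), and the IV dose contributes 300 × e^(−kt). Summing over doses on Days 1, 8, 36 and 64 gives relative levels of 180 on Day 64 before dosing, 366 on Day 71, 176 on Day 92 and 16 on Day 154. Day 92 is therefore at about the earlier on-treatment trough (176 against 180) and at 176/366 = 48% of the Day 71 level. Day 154 is at 16/366 = 4%. The contradiction does not depend on this model.

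**5. What the sections tell a site to do with an event on, say, Day 110.**

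| Event | General rules | Post-EOT rule in 9.6.3 | Outcome |
|---|---|---|---|
| Related, nonserious AE | Enter (9.4, 9.6.1) | Silent | Entered |
| Related SAE, not an AESI | Enter (9.4, 9.6.1, 9.6.3) | Report to sponsor; do not enter | Direct conflict; barred if the specific rule is followed |
| Related, serious AESI | Enter and expedite (9.6.2) | Report to sponsor; do not enter | Opposite instructions |
| Unrelated AESI | Enter and expedite (9.6.2, no causality condition) | Silent | Entered |
| Unrelated SAE, not an AESI | Enter (9.4, 9.6.1, 9.6.3) | Silent | Entered, unless the site takes 8.5.5 to end participation at Day 92 |

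**6. After collection.** An event barred from the eCRF is absent from the AE and SAE listings in SAP 11.2. An event that is entered but starts after Day 92 is listed, yet it falls outside the SAP's TEAE window and so outside the by-arm tables.

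**7. Number of events.** The documents give no SAE rate in IPF for these 62 days. Purely as an assumption, a 1% to 10% per-subject risk of any SAE in the window, with 70 subjects, gives 70 × 0.01 = 0.7 to 70 × 0.10 = 7 subjects. Only those with an SAE judged related fall under the explicit bar.

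**The case against.** The strongest reply is that most of the protocol already states the intended collection. Observation runs to the call, the call collects AEs, all AEs and AESIs go into the eCRF, and 9.6.3 itself requires all SAEs during a study that does not end until the call. Section 8.5.5 is the outlier, and 8.5.6 contradicts it. Related late SAEs still reach the sponsor within 24 hours, so the sponsor is not left unaware. Whether its safety data are later reconciled with the clinical data cannot be seen from these documents. All of this stands. It limits the scope but leaves the explicit bar on related SAEs untouched.

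Four stronger readings might be inferred, and the documents do not support them:

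- **SAE collection narrows to related events after Day 92.** Section 9.6.3 never says that unrelated SAEs stop being collected. Their loss is an inference from 8.5.5, helped by the instruction in 9.6.3 to send follow-up information to the sponsor once a subject has left the study.
- **An unrelated pulmonary embolism on Day 110 would go unreported.** A thromboembolic event is an AESI, and 9.6.2 requires every AESI to be entered and expedited with no causality condition.
- **The individual halting criteria in 3.9.1 raise the stakes.** They pause further dosing, and dosing is complete by Day 64.
- **Correcting 9.6.3 alone would complete SAE incidence by arm.** It would complete the listings only, because SAP 11.2 ends summarised TEAEs at Day 92.

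**Conclusion.** The concern holds in a limited form. For 62 days (55 to 69), SAEs judged related are explicitly kept out of the eCRF while 9.4, 9.6.1, 9.6.2 and the general rule in 9.6.3 require them there. Serious related AESIs receive contradictory instructions. The loss is from the clinical database and the SAP listings, not from sponsor reporting. Unrelated SAEs are exposed only if sites act on 8.5.5 as written.

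The length of the window rests on the stated visit days. That it matters rests on the dosing schedule, which puts Day 92 at a trough. The number of events lost is unknown, and the 0.7 to 7 subjects above is an assumed range for any SAE, not an estimate of the loss. The contradiction affects the primary endpoint and is cheap to remove, so it should be settled before database lock.

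**What to change.** 1. In protocol 9.6.3, change the trigger of the rule for late related SAEs from the EOT Visit to the Follow-up Telephone Call, matching 9.4. All SAEs up to the call then go into the eCRF, and the conflict with 9.6.2 disappears. The gap in capture falls from 62 days to 0.
2. In protocol 8.5.5, state that participation ends with the Follow-up Telephone Call.
3. Ask sites to enter retrospectively any SAE between Day 92 and Day 154 already reported outside the eCRF.
4. Reconcile the TEAE end in SAP 11.2 (end of the Treatment and Observation Period, Day 92) with protocol 10.3.3 (no end date), so that these events are tabulated by arm as well as listed.

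The cost is wording in a protocol amendment and the SAP, a site memo and a few more eCRF entries. The Day 154 call and the AE page of the eCRF already exist.

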9.6.4 Other Significant Events

Not applicable.

9.6.5 Overdose

Any overdose that occurs in association with an adverse sign or symptom must be entered into the eCRF as an AE; if the AE meets any seriousness criteria, the event must be reported as an SAE (see [Section 9.6.3](#)).

Details (ie, volume, location of infusions, infusion rate) of overdose of investigational product (defined in [Section 5.1.3.3](#)) must be recorded in the study treatment administration eCRF. Details of overdose of any concomitant therapy must be recorded in the Concomitant Medication eCRF.

9.6.6 Pregnancy and Breastfeeding

A female subject or female partner of a male subject who becomes pregnant while participating in the study, or up to and including 90 days after the last administration of investigational product, must notify the investigator immediately.

If a female subject becomes pregnant, she must discontinue treatment with investigational product, but may continue other study procedures at the discretion of the investigator. If the female subject is in the active treatment period of the study, her participation will be discontinued and the procedure for discontinuation of a subject will be followed, as described in [Section 4.3](#)).

CSL must be notified within 5 days of the investigator becoming aware of the pregnancy.

Whenever possible, a pregnancy in a subject or in a female partner of a male subject exposed to investigational product should be followed to term so as to assess any potential occurrence of congenital anomalies or birth defects. Any follow-up information, including premature termination and the status of the mother and child after delivery, should be reported by the investigator to CSL using a Pregnancy Reporting / Outcome Form.

9.7 Institutional Review Board / Independent Ethics Committee Reporting Requirements

The time frame within which an IRB / IEC must be notified of deaths and investigational product-related unexpected SAEs is stipulated by each IRB / IEC. It is the investigator's responsibility to comply with the requirements for IRB / IEC notification. CSL will provide investigators with all details of all SAEs reported to health authorities.

10 Statistics

10.1 Sample Size Estimation

The sample size for this study was determined based on feasibility, not based on a power calculation. It was estimated that enrolling approximately 80 subjects (40 in each treatment group), and taking into account a 12% dropout rate, a total of 70 evaluable subjects (35 in each treatment group), would be considered sufficient for assessment of safety, PK, and biomarker profiles.

10.2 Description of Study Analysis Sets

10.2.1 Screened Analysis Set

The Screened Analysis Set comprises all subjects who provide written informed consent and who complete all of the Screening procedures.

10.2.2 Safety Analysis Set

The Safety Analysis Set comprises all subjects who receive any portion of an IV infusion or SC injection of CSL312 or placebo, and analyses will be based on the actual treatment received.

10.2.3 Pharmacokinetic Analysis Set

The PK Analysis Set is defined as subjects in the Safety Analysis Set who receive ≥ 1 dose of CSL312 with ≥ 1 measurable concentration of CSL312 after administration.

10.2.4 Pharmacodynamic Analysis Set

The PD Analysis Set is defined as subjects in the Safety Analysis Set for whom analysis results are obtained for ≥ 1 of the exploratory biomarkers of interest.

10.3 Statistical Analyses and Methods

10.3.1 General Considerations

A complete description of the statistical analyses and methods will be provided in the statistical analysis plan (SAP), which will be finalized before database lock. In general, continuous variables will be summarized using descriptive statistics (number of observations [n], mean, SD, median, minimum and maximum. Categorical variables will be described using frequencies and percentages. For repeated observations of continuous variables, the change from Baseline will also be summarized.

All statistical tests will be 2-sided and will be performed at the 5% level of significance. Since no type I error adjustment will be performed for this study, all p-values will be considered nominal.

If not specified otherwise, Baseline refers to the last nonmissing measurement before the first administration of investigational product (CSL312 or placebo).

